10.4 Analysis Population

N/A

10.5 Effectiveness Analysis

Effectiveness will be assessed through pain and quality of life questionnaires (VAS/ OPAS/ IDEEL) Questionnaires regarding changes or reduction in the current systemic medications will be applied and used as a clinical effective parameter.

10.6 Safety Analysis

The primary safety variable monitored will be the occurrence of adverse events. The severity of each adverse event observed will be evaluated as serious or not serious as defined by the Tufts

Tufts Medical Center

HSC and the occurrence will be evaluated as expected or unexpected. The relationship of the event to the study medication will be assessed by the investigator as possibly, probably, or definitely related. Safety variables will be evaluated at screening and at all study visits. If adverse events occur, the first concern will be the safety of the study participants. Any serious adverse event occurring during the study period will be immediately reported to Tufts IRB. Directed questioning will be done to assess tolerability. Additional steps taken to assess safety will be followed as outlined in section 8.1 of this SUPP M form.

10.7 Interim Analysis

N/A

11. DATA AND SAFETY MONITORING

11.1 Data and Safety Monitoring Plan

The PI, research fellows, research coordinators, and technicians involved with this protocol will be required to read the protocol, participate in a group meeting to discuss roles before the protocol is approved, and participate in weekly clinical research meetings. The pharmacy and the clinical fellows on the protocol will be required to read the protocol and separate meetings will be created to discuss roles as they relate to the protocol.

A copy of the approved protocol and study related materials will be placed on a shared network drive accessible to authorized research staff involved in this study and on IRBnet.org.

The primary safety variable monitored will be the occurrence of adverse events. The severity of each adverse event observed will be evaluated as outlined in section 10.6 by the treating investigator. The PI will be made aware of all AEs within one week. The ocular surface exam and IVCM imaging will only be performed by a research technician, fellow, or investigator to ensure adherence to the required tests and accurate assessments.

The study coordinator will be responsible for monitoring each visit to ensure that the procedures are performed as outlined in the protocol and documented appropriately.

Raw data collected for this study will be entered into a master database by the study coordinator, research technician, or fellow and uploaded for access to the principal investigator and all authorized research staff members on the U-Drive of password-protected computers located in the Cornea Research Department.

12. DATA HANDLING, RECORD-KEEPING AND MONITORING

12.1 Data Recording, Record-Keeping and Monitoring

A Case Report Form (CRF) will be completed for each subject enrolled into the clinical study. The Investigator will review, approve and sign/date each completed CRF; the Investigator's signature serving as attestation of the responsibility for ensuring that all clinical data entered on the CRF are complete, accurate and authentic.

The LMR will be considered Source Data and will contain the clinical findings and observations, and other information collected during the visit. Subject consents will be maintained within the Department of Ophthalmology Clinical Research Office.

All data will be stored on in the G-drive located on encrypted, password protected computers in the Cornea Research Department. Only the PI and researchers specific to this study who have been granted access to the data by the PI will be able to view the data in the TUFTS network protected folder. When data is sent out to be analyzed the data will be de-identified. The data will contain subject identification numbers, which are linked to identifiers on a separately secured spreadsheet. The data will be coded by assigning each participant a subject identification number and removing any identifiable information. The code will be secured by the PI and Study Coordinator in in the U-drive located on encrypted, password protected computers in the Cornea Research Department. The code that links information that can identify the participant to the data collected for this research will be kept separate from their health information, which will be destroyed once this study is complete and the manuscript has been published.

Study data are boxed and logged when the study is terminated and housed in on-site locked room until the 7 year requirement is met, and then transferred to off-site storage.

13. STUDY DISCONTINUATION CRITERIA

13.1 Discontinuation of Individual Research Subjects

Please see sections 9.3.

Appendix I: Ocular Surface Disease Index (OSDI)

Have you experienced any of the following during the last week:

	All of the time	Most of the time	Half of the time	Some of the time	None of the time
1. Eyes that are sensitive to light?	4	3	2	1	0
2. Eyes that feel gritty?	4	3	2	1	0
3. Painful or sore eyes?	4	3	2	1	0
4. Blurred vision?	4	3	2	1	0
5. Poor vision?	4	3	2	1	0

Have problems with your eyes limited you in performing any of the following during the last week:

	All of the time	Most of the time	Half of the time	Some of the time	None of the time	
6. Reading?	4	3	2	1	0	N/A
7. Driving at night?	4	3	2	1	0	N/A
8. Working with a computer or bank machine (ATM)?	4	3	2	1	0	N/A
9. Watching TV?	4	3	2	1	0	N/A

Have your eyes felt uncomfortable in any of the following situations during the last week:

	All of the time	Most of the time	Half of the time	Some of the time	None of the time	
10. Windy conditions?	4	3	2	1	0	N/A
11. Places or areas with low humidity (very dry)?	4	3	2	1	0	N/A
12. Areas that are air conditioned?	4	3	2	1	0	N/A

Total score for answers 1 to 12: _____

Total number of questions answered: _____

(Do not include questions answered N/A)

OSDI = (sum of scores) x 25/(# of questions answered): _____

Appendix II: Cornea Fluorescein Staining

[figure not shown]
Fluorescein instillation:

Fluorescein strip wetted with buffered saline. Drop instilled on inferior palpebral conjunctiva. The participant is asked to blink several times.

[figure not shown]
Staining:

5 corneal regions (shown below) will be graded with a staining scale of 0-3. The “total scores” of the cornea and each region will be measured.

Corneal Fluorescein Staining: (0 – 3 for each of 5 zones)

Lissamine Green Staining: (0 – 3 for each zone)

[figure not shown]
Appendix III: Ocular Pain Assessment Scale (OPAS) questionnaire

Ocular Pain Assessment Survey (OPAS) © 2013 Massachusetts Eye and Ear Infirmary

[figure not shown]
Please fill this form **only if** you HAVE EYE/FACIAL PAIN today or HAVE FILLED THIS FORM BEFORE

[Patient information sticker]

1. Please rate the overall severity of your pain today: (0= no pain, 10= worst pain ever)

2. On the diagram below, please shade the area where you have eye pain, and/or pain in the face and head region.

[figure not shown]

3. Do you have any longstanding pain elsewhere in your body? NO If yes, please state where: _____

[figure not shown]
ALL QUESTIONS REFER TO PAIN IN YOUR WORSE EYE. Please circle the level of your eye pain for the following:

EYE PAIN INTENSITY 24 HOURS

[figure not shown]
Level of eye pain when it is **MOST** painful:

Level of eye pain when it is **LEAST** painful:

[figure not shown]

Level of eye pain on **AVERAGE**:

[figure not shown]

EYE PAIN INTENSITY 2 WEEKS

[figure not shown]
7. in the past 2 weeks

8. in the past 2 weeks

[figure not shown]
[figure not shown]

9. in the past 2 weeks

NON-EYE PAIN

Please circle the level of your **worst non-eye pain** (pain at temples, back of head, cheek area):

Please circle the percentage of time you spend thinking about your **non-eye pain (face/head)**:

12. **Not at all** **All the time**

Tufts Medical Center

Ocular Pain Assessment Survey (OPAS) © 2013 Massachusetts Eye and Ear Infirmary

QUALITY OF LIFE (QOL)

Please circle one number that describes how much your pain has interfered with/affected the following:

Reading and/or Computer use														
13.	Not at all	0	1	2	3	4	5	6	7	8	9	10	Completely	 N/A

Driving and/or Watching TV														
14.	Not at all	0	1	2	3	4	5	6	7	8	9	10	Completely	 N/A

General activity (walking, doing house chores)														
15.	Not at all	0	1	2	3	4	5	6	7	8	9	10	Completely	 N/A

Mood														
16.	Not at all	0	1	2	3	4	5	6	7	8	9	10	Completely	 N/A

Sleep														
17.	Not at all	0	1	2	3	4	5	6	7	8	9	10	Completely	 N/A

Enjoying life/Relations with other people														
18.	Not at all	0	1	2	3	4	5	6	7	8	9	10	Completely	 N/A

Please circle the percentage of time you spend thinking about your eye pain:

19.	Not at all	0%	50%	100%	All the time
-----	------------	----	-----	------	--------------

AGGRAVATING FACTORS

Please circle how much your pain is increased when exposed to:

Wind, dry air, heat, air conditioning					
20.	No change	0%	50%	100%	Severe increase

Volatile chemicals (cleaning agents, fumes, cosmetic fragrances)					
21.	No change	0%	50%	100%	Severe increase

ASSOCIATED FACTORS

Please circle **how often** your eye pain is accompanied by the following symptoms:

Redness					
22.	Never	0%	50%	100%	All the time

Burning					
23.	Never	0%	50%	100%	All the time

Sensitivity to light					
24.	Never	0%	50%	100%	All the time

Tearing					
25.	Never	0%	50%	100%	All the time

[figure not shown]
SYMPTOM RELIEF

Please circle **how much pain relief** you have experienced since the last visit:

Eye pain													
26.	No relief	0%	10%	20%	30%	40%	50%	60%	70%	80%	90%	100%	Complete relief  N/A

Non-eye pain (face/head)													
27.	No relief	0%	10%	20%	30%	40%	50%	60%	70%	80%	90%	100%	Complete relief  N/A

Appendix IV: Visual Analogue Scale questionnaire

Appendix V: IDEEL QoL questionnaire

Daily Activities

- The following is a list of day-to-day activities that you may or may not have participated in **OVER THE LAST TWO WEEKS**.
- If you participated in the activity, please choose how often you were **limited in or stopped doing the activity BECAUSE OF YOUR DRY EYES**.
- Choose 'I did not perform this activity due to reasons OTHER than dry eye' if you did not take part in the activity for reasons other than your dry eyes.
- Please choose only one box per question.

OVER THE LAST TWO WEEKS, how limited were you in doing the following activities BECAUSE OF YOUR DRY EYES?
	
I did not do this activity for reasons OTHER than my dry eyes/Not applicable (5)
	
OVER THE LAST TWO WEEKS I was limited BECAUSE OF MY DRY EYES:
						
I can no longer do this activity due to my dry eyes (0)

		None of the time (5)	A little of the time (4)	Some of the time (3)	Most of the time (2)	All of the time (1)		
1. Doing close work in the morning or afternoon (such as crossword puzzles, reading, looking at a computer, and/or sewing)								
2. Doing close work in the evening or at night								
3. Driving								
4. Being around and/or using scented products (such as cologne or hairspray)								
5. Working on a computer								
6. Going somewhere where there is tobacco smoke								

		OVER THE LAST TWO WEEKS I was limited BECAUSE OF MY DRY EYES:						
OVER THE LAST TWO WEEKS , how limited were you in doing the following activities BECAUSE OF YOUR DRY EYES?		I did not do this activity for reasons OTHER than my dry eyes/Not applicable (5)	None of the time (5)	A little of the time (4)	Some of the time (3)	Most of the time (2)	All of the time (1)	I can no longer do this activity due to my dry eyes (0)
or being around someone who smokes								
7. Wearing contact lenses								
8. Wearing make-up near or on my eyes								
9. Flying on an airplane								

Feelings

The following questions ask about how dry eye affected your mood and social life **OVER THE LAST TWO WEEKS**. Please choose how **often** you experienced each **feeling** **BECAUSE OF YOUR DRY EYES**. Please choose only one box per question.

OVER THE LAST TWO WEEKS , how often do you have each of the following feelings BECAUSE OF YOUR DRY EYES?		OVER THE LAST TWO WEEKS , I experienced this feeling BECAUSE OF MY DRY EYES:				
		None of the time (4)	A little of the time (3)	Some of the time (2)	Most of the time (1)	All of the time (0)

Tufts Medical Center

OVER THE LAST TWO WEEKS, how often do you have each of the following feelings BECAUSE OF YOUR DRY EYES?
		
OVER THE LAST TWO WEEKS, I experienced this feeling BECAUSE OF MY DRY EYES:
				
		None of the time (4)	A little of the time (3)	Some of the time (2)	Most of the time (1)	All of the time (0)
10. Irritability						
11. Impatience						
12. Feeling sad						
13. Worry that my dry eyes will get worse						
14. Feeling annoyed						
15. Feeling like my eyes do not look nice						
16. Feeling like I have to make adjustments to my life						
17. Feeling different from other people because of my dry eyes						
18. Feeling like I am always aware of my eyes						
19. Feeling older than I really am						
20. Feeling like people look at me and think I am fine when I'm not						
21. Feeling like there is nothing I can do for my dry eyes						

Work

22. Are you currently working?

Yes If "Yes," please read the instructions below.

No

The following questions ask about how often your dry eyes affected your work life **OVER THE LAST TWO WEEKS**. Please choose how **often** you experienced the following situations **at work BECAUSE OF YOUR DRY EYES**. Please choose only one box per question.

		OVER THE LAST TWO WEEKS I experienced the following situation at work BECAUSE OF MY DRY EYES:				
OVER THE LAST TWO WEEKS , how often did you experience the following situations at work BECAUSE OF YOUR DRY EYES?		None of the time (4)	A little of the time (3)	Some of the time (2)	Most of the time (1)	All of the time (0)
23. Feeling distracted						
24. Feeling like I couldn't concentrate						
25. Having to take a break from work						
26. Having to change the way I work (such as the way I read, look at a computer, or work outside)						
27. Having to change my work environment (such as how close I am to an air conditioning or heating vent)						

Thank you for finishing this questionnaire.
Please make sure that you answered every question.

Appendix VI: Ocular Tolerability and Compliance Questionnaire

After you used the TrueTear® neurostimulation, how intensely have you experienced the following symptoms?

Itching

Right Eye:	None	Trace	Mild	Moderate	Severe
Left Eye:	None	Trace	Mild	Moderate	Severe

Burning Sensation

Right Eye:	None	Trace	Mild	Moderate	Severe
Left Eye:	None	Trace	Mild	Moderate	Severe

Foreign Body Sensation

Right Eye:	None	Trace	Mild	Moderate	Severe
Left Eye:	None	Trace	Mild	Moderate	Severe

Have you experienced any other symptoms after undergoing the study tests?

YES NO

If yes, which one(s) _____

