6. BIOSPECIMEN COLLECTION (IF APPLICABLE)

6.1 Specimen preparation, handling, and shipping: N/A

6.2 Instruction for specimen preparation, handling and storage: N/A

6.3 Specimen shipment: N/A

6.4 Future use of stored specimens: N/A

7. STUDY PROCEDURES

7.1 Screening/Baseline Procedures

Prospective participants, as defined by the inclusion/exclusion criteria, will be considered for entry into this study. Concurrent enrollment of subjects who are participants in other studies will be allowed based on the investigator's discretion.

During the consent process, study design and treatment regimen will be discussed with each subject. Written informed consent will be obtained before any study specific procedures are performed. However, standard of care clinical information (such as: medical history, BCVA, TBUT, staining, and Schirmer's test) obtained during a subject's clinical visit within the previous 48 hours can be used during the screening visit to determine eligibility and as their baseline assessments.

The following evaluations and procedures will be performed for all subjects during the screening period:

- Written informed consent
- Record of current ocular and systemic medications
- Record of significant medical/surgical history in the past 5 years
- Record of demographic data, including date of birth, sex, and race/ethnicity
- Eye examination (best corrected visual acuity, slit-lamp biomicroscopy, intraocular pressure)
- Corneal fluorescein staining
- Conjunctival lissamine green staining
- Tear break-up time (TBUT)
- Corneal *in vivo* confocal microscopy (IVCM)
- Ocular Surface Disease Index (OSDI) questionnaire
- Ocular Pain Assessment Survey (OPAS) questionnaire
- IDEEL QoL Questionnaire
- The following evaluations and procedures will be performed for all subjects during the Enrollment/Baseline procedures (once the patient is confirmed to be eligible): Visual Analogue Scale (VAS) questionnaire before and after each of the five tests (filter glasses response, hyperosmolar saline response, cold saline response, proparacaine challenge test) Schirmer's test II (with anesthesia)

The description of the procedures is as follows:

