Filter glasses: This test will be done in a dimly lit room, about 50 lumens of light intensity (approximately 50-75 square feet room with 10 lumens per square feet), room temperature, pressure and humidity. Each eye will be assessed separately. The other eye will be covered with an occluder to eliminate exposure to the light. The study eye will be covered using a 100% opaque filter and then the opacity of the filters will be reduced in decrements of 10%. Ten graded filters have been developed for this purpose; each of these filters decrease light opacity by 10%. Light will be shone at a distance of approximately 10 cm from the eye, using a mussel light (halogen fiber-optic transilluminator). Starting at the 100% opaque filter, the filter at which the patient starts to feel pain/photophobia will be noted. That light level will be used to assess threshold and a pain/photophobia for each filter will be noted on a scale of 1-10. Using pilot studies we have seen that the pain/burning can increase with an increase in light in patients with NCP.

Cold Response Test: One drop of cold 0.9% preservative-free saline eye drops will be topically applied onto the patient's eyes. The level of discomfort/pain will be assessed by the VAS questionnaire before and after the drops are applied.

Hyperosmolality Response: One drop of 5% sodium chloride (Muro 128® 5%) drop will be topically applied on the conjunctival fornix of both eyes. The level of discomfort will be measured the VAS questionnaire before and after application of a 5% sodium chloride drop.

Proparacaine Challenge Test: One drop of Proparacaine Hydrochloride Ophthalmic Solution 0.5% will be topically applied in both eyes to differentiate between the peripheral versus central

Tufts Medical Center

component of the patient's pain or discomfort. The level of discomfort/pain will be assessed by the VAS questionnaire.

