7.2 Study Visit

The study will be performed in four visits. During the baseline visit, all patients will be evaluated using the flowchart (page 2). The first visit will include in-office testing of ITN and response to ITN. After 45 days (6 weeks \pm 1 week) and 90 days (3 months \pm 2 weeks) of using the ITN on a daily basis, the patients will return for follow-up visits. The same flowchart as for screening visit will be followed in these two visits (with the exception confocal microscopy on visit 2). Additionally, evaluation of diary for daily use (Appendix VII) and questionnaires regarding

Tufts Medical Center

tolerability and safety of device and any reduction in the use of concomitant pain medications will be assessed on these visits.

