7.4 Follow-up Procedures

Subjects will come back for a 1st visit after the screening visit; 2nd visit at 45 days (\pm 1 week) following the first visit, and 3rd visit following 90 days after the first visit (\pm 2 weeks). All of the procedures done at the baseline visit will be done in the 2nd and 3rd visits (see flowchart).

In addition, subjects will be asked about their usage of the ITN. Ocular safety and tolerability questionnaire (appendix VI) will be administered in the 2nd and 3rd visit. The subject will be asked to complete a diary every day to record any pain symptoms (Appendix VII). The subject will be asked to send their pain diary weekly to the study coordinator, in however method works for the subject to ensure compliance with the ITN. They will also need to bring the diary to each study visit, to ensure compliance.

Ocular Tolerability Questionnaire (Appendix VI): This questionnaire assesses tolerability of the ITN device. It assesses symptoms of discomfort in each eye after ITN use.

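### The only open item on the device tolerability form asks about symptoms after the study tests, not after use of the device

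*Combined protocol and SAP*

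**What the plan says.** Section 10.2 lists tolerability as a secondary outcome, on a separate line from safety. Section 10.6 states: "Directed questioning will be done to assess tolerability". Section 5.2 has the investigator or research staff put Appendix VI to participants as directed questioning. Section 7.4 (Follow-up Procedures) gives the form's purpose, "This questionnaire assesses tolerability of the ITN device", and schedules it for visits 2 and 3, at 45 and 90 days.

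The graded part of Appendix VI opens with "After you used the TrueTear® neurostimulation, how intensely have you experienced the following symptoms". It covers itching, burning and foreign body sensation, each eye separately, from none to severe. One open item follows: "Have you experienced any other symptoms after undergoing the study tests". It has a yes/no answer and a line for naming the symptoms.

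On what a test is, section 7.1 asks for VAS ratings before and after "each of the five tests (filter glasses response, hyperosmolar saline response, cold saline response, proparacaine challenge test". (The text says five and names four.) On when the tests recur, section 7.4 (Follow-up Procedures) says "All of the procedures done at the baseline visit will be done in the 2nd and 3rd visits (see flowchart".

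**The concern.** The graded items and the open item on one short form ask about different exposures. The graded items concern the device. The open item, which should catch whatever the three listed symptoms miss, concerns the study tests. A participant who takes it at its word would report stinging from a saline drop or pain from the light, and would not be prompted to mention a symptom that follows use of the device at home.

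The open item matters more here because the graded list is narrow. The device is placed in both nostrils (section 5.3), its hydrogel tip touches the inside of the nose (section 5.1), and the exclusion criteria in section 4.2 include nosebleeds and hypersensitivity to that hydrogel. Yet the form has no nasal item. On this form, the open question is the only place where a nasal or other unlisted device symptom could be written down.

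At stake is what the directed instrument for a secondary outcome measures. The primary endpoint is not involved.

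**Working it through.** No arithmetic applies. The point concerns the wording of one item and depends on no sample size, rate or effect size. The check sets the relevant places side by side.

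1. **Items by exposure.** Appendix VI has three graded symptoms tied to device use, one open item tied to the study tests, and no open item tied to device use.

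2. **Stated purpose.** Section 7.4 (Follow-up Procedures) describes the form as a measure of device tolerability and of eye discomfort following ITN use. The graded stem matches this purpose and the open item does not.

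3. **Meaning of study tests.** The form does not define the term. The nearest usage is in section 7.1, where tests means the filter-glasses, hyperosmolar saline, cold saline and proparacaine challenges. These apply light or drops to the eye and are not part of using the device.

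4. **A wider reading.** Section 7.2 says: "The first visit will include in-office testing of ITN and response to ITN". Section 7.4 (Study Specific Procedures) lists the ITN response at 1 and 3 minutes. If the term is stretched to include these, it reaches use of the device in the clinic. It still does not reach home use, which section 5.3 sets at twice a day or more and which fills the interval before visits 2 and 3.

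5. **Timing.** The form is given at visits 2 and 3, and the baseline procedures are repeated at those visits. Participants answering it have therefore had both exposures: home use of the device and one or more rounds of challenges.

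6. **What an answer then contains.** If a participant follows the printed words, the entry is a test reaction. If the participant reads the item as continuing the list above it, the entry is a device symptom. The form has no field that records which of the two was meant.

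7. **Other routes for the same information.**
   - Section 8.1 requires a general, non-directed opening question at every visit. One of its examples covers the time since the previous visit.
   - Section 9.1 records all observed or volunteered events and requires an assessment of their relation to the device.
   - The diary in Appendix VII rates discomfort, pain and photosensitivity before and after ITN use. Its daily page covers redness, burning, light sensitivity and tearing, though not by reference to the device. The diary text available shows no open question on device symptoms.

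**The case against.** The strongest reply is that this is a slip in one line with little practical effect. Staff ask the questions (section 5.2) and can explain which exposure is meant. The words *any other* come straight after three device-related items, so many participants will take the open item as part of the same list. Reactions to the saline challenge are captured elsewhere, since "The level of discomfort will be measured the VAS questionnaire before and after application of a 5% sodium chloride drop", and that record can be set against the free text. Section 7.4 also describes the form in terms of eye discomfort, so it may never have been meant to cover the nose.

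Most of this stands, and it limits the size of the point. It does not remove it. An interviewer's clarification is not written into the plan and may differ between staff. A participant who reads the item generously gives an answer that shares a line with test reactions. The open item is not restricted to the eyes, and the form is said to assess tolerability of the device as a whole.

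A reader might infer more, and the documents do not support it:

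- *That unlisted device symptoms are lost to the trial.* Sections 8.1 and 9.1 and the diary provide other routes.
- *That the entries can never be separated afterwards.* A participant who names a nasal symptom, or stinging from a drop, has partly shown the cause.
- *That the tolerability result is biased by a stated amount or in a known direction.* No rates of device symptoms or test reactions are given, and section 10.2 says only that tolerability is an outcome. No count of other symptoms is defined as an endpoint.
- *That the form follows the day's challenges and so picks up fresh stinging.* The order within the visit depends on a flowchart that is not in the text available, so it cannot be judged.

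**Conclusion.** The point holds as a minor one. The open item of Appendix VI asks about an exposure that does not fit the form's graded stem or its stated purpose, and no reading of study tests extends to home use. As printed, the directed instrument for a secondary outcome does not ask for unlisted device symptoms, and what it collects under that item can be a mixture.

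The conclusion rests on two readings. The first is that the directed questioning in section 10.6 is the Appendix VI questionnaire. Section 10.6 does not name the form, but sections 5.2 and 7.4 support the link. The second is that tests on the form has the meaning it has in section 7.1. If the second is relaxed to include ITN testing in the clinic, the gap for home use remains.

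The size cannot be given as a number. It is confined to one item of one secondary, descriptive measure in a single-arm pilot.

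**What to change.** Reword the open item so that it refers to the device and to the interval since the previous visit, for example: *Since your last visit, have you had any other symptoms during or after using the TrueTear device? Which, and how intense (None/Trace/Mild/Moderate/Severe)?* This uses the form's existing grades and lets participants report nasal symptoms.

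If reactions to the study tests are wanted on this form, ask about them in a separate item and do not count the answers as device tolerability.

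The cost is one reworded line and at most one added line, with no new procedure or visit.
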